7.1 General Considerations for Data Analyses

All analyses will be performed with using SAS Version 9.4. All analysis output will use the following treatment group naming conventions and treatment order:

ER group: patients will receive ER (details in procedure part) plus medical treatment (same as the control group);

Medical group: patients will receive the medical treatment alone.

All statistics is two sided with a $P < 0.05$ considered significant.

Examination of Subgroups

The rates of the primary outcome will be presented for each level of the covariates listed below. We will assess the extent to which the treatment effect varies across levels of each subgroup using interaction tests.

Multiple Comparisons and Multiplicity

A single primary efficacy variable has been defined for this study, with all other efficacy variables identified as secondary or other. Similarly, only one treatment comparison is of interest in the study and therefore there are no requirements to adjust for multiple comparisons or multiple endpoints within this study.

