3.9.2 Secondary outcomes

Secondary outcomes as follows:

- Mortality within 1 year;
- Ischemic stroke outside the territory of the qualifying artery within 1 year;
- Disabling stroke within 1 year;
- TIA in the territory of the qualifying artery within 1 year;
- Unplanned revascularization (EC-IC bypass surgery or ER) of the qualifying artery within 1 year;
- Myocardial infarction within 1 year;
- Composite vascular events within 1 year;
- Quality of life assessment (EuroQol -Five-Dimensions [EQ-5D] scale questionnaire) at 1 year;
- mRS score at 1 year;
- Periprocedural outcomes;
- Restenosis or reocclusion (symptomatic or asymptomatic).

Disabling stroke is defined by any of the following: (1) an mRS score of 3 or more, (2) an increase of at least 1 point in the mRS score from prestroke baseline, (3) a score on the composite NIHSS of 7 or more, or (4) an increase of at least 4 points in the NIHSS score from pre-stroke baseline.

TIA is defined as duration of a focal or global neurological deficit <24 hours, any variable neuroimaging does not demonstrate a new hemorrhage or infarction.

Composite vascular events within 1 year included any stroke, myocardial infarction, and unplanned revascularization within 1 year.

Periprocedural outcomes are: (1) successful recanalization rate, (2) periprocedural complications: in-stent thrombosis, distal embolization, symptomatic intracranial hemorrhage, parenchymal hematoma type 2 (defined by the Heidelberg classification³⁴), arterial dissection, arterial perforation, (3) residual stenosis, (4) NIHSS score at 24-72 hours, (5) death within 7 days.

Restenosis is defined as >50% stenosis within or immediately adjacent (within 5 mm) of the treated segment and >20% absolute luminal loss, reocclusion is defined as total occlusion of the target artery segment.

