3.16.5 Statistical Significance and Software

All statistical tests are performed by 2-sided tests. A 2-sided P value less than 0.05 is considered to demonstrate a statistically significant difference. All analyses will be performed with SAS software version 9.4 (SAS Institute).

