5.2. Secondary Outcomes

The secondary outcomes are as follows:

- (1) Mortality within 1 year;
- (2) Ischemic stroke outside the territory of the qualifying artery within 1 year;
- (3) Disabling stroke within 1 year;
- (4) Transient ischemic attack (TIA) in the territory of the qualifying artery within 1 year;
- (5) Unplanned revascularization (extracranial-intracranial [EC-IC] bypass surgery or ER) of the qualifying artery within 1 year;
- (6) Myocardial infarction within 1 year;
- (7) Composite vascular events within 1 year, including any stroke, myocardial infarction, and unplanned revascularization;
- (8) Quality of life assessment (EuroQol-Five-Dimensions [EQ-5D] scale questionnaire) at 1 year;
- (9) Modified Rankin Scale (mRS) score at 1 year;
- (10) Periprocedural outcomes, including the successful recanalization rate, periprocedural complications, residual stenosis, National Institute of Health Stroke Scale (NIHSS) score at 24-72 hours, death within 7 days, etc;
- (11) Restenosis or reocclusion (symptomatic or asymptomatic).

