7.5 Safety Analyses

Summary tables and data displays will be provided for adverse events as well as serious adverse events (as detailed in the study protocol). Procedure-related complications in the endovascular recanalization group will be analyzed. The Chi-square test or Fisher's exact test will be used to compare the incidence of adverse events and serious adverse events between the treatment groups.

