7.6 Propensity Score Matching Analysis

Propensity score matching (PSM)² will be performed to reduce the possible influence of selection bias and confounders on the outcomes. A PSM cohort will be established in a 1:1 ratio based on the nearest-neighbor matching algorithm with a caliper width of 0.2 of the propensity score with main variables associated with the primary outcome as covariates. Statistical analysis methods for baseline characteristics and outcome will remain consistent before and after PSM.

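### SAP 7.1 waives multiplicity control because there is one primary variable, yet its blanket P<0.05 rule also covers nine comparative secondary outcomes and 12 interaction tests, none labelled exploratory

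*SAP*

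**What the plan says.** - **Significance rule.** SAP 7.1: "All statistics is two sided with a $P < 0.05$ considered significant". Protocol 3.16.5: "A 2-sided P value less than 0.05 is considered to demonstrate a statistically significant difference". The Statistical Methods row of the protocol synopsis repeats the rule. None of the three limits it to the primary outcome.
- **Multiplicity.** SAP 7.1 starts from the premise that "A single primary efficacy variable has been defined for this study, with all other efficacy variables identified as secondary or other", adds that only one treatment comparison is of interest, and concludes that "there are no requirements to adjust for multiple comparisons or multiple endpoints within this study".
- **Secondary outcomes.** SAP 5.2 lists 11. SAP 7.7 Secondary Outcomes assigns them Cox, logistic, ordinal logistic or linear models.
- **Subgroups.** SAP 7.6 Subgroup Analysis lists 11 factors, one of them (time from the latest event) split at two cut-points. Each interaction gets its own Cox model, whose stated purpose is to judge significance.
- **Matching.** SAP 7.6 Propensity Score Matching Analysis: "Statistical analysis methods for baseline characteristics and outcome will remain consistent before and after PSM". Protocol 3.16.4 says the same.

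**The concern.** A single primary variable is a good reason not to adjust the primary test for other endpoints. It says nothing about the error rate among the other tests. The plan carries the no-adjustment conclusion over to the whole study and keeps a rule under which any P<0.05 counts as significant. The label of secondary or other has no stated consequence: there is no testing order, no adjusted level and no exploratory label.

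What is at stake is the standing of secondary and subgroup findings. Under the plan as written, a chance result on TIA, or an interaction with diabetes, may be declared significant on the same terms as the primary result.

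**Working it through.** The documents give no familywise error rate, sample size or event count, so there is no figure of the plan's own to reproduce. The only numerical input is the two-sided level of 0.05.

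**Counting the tests**

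- *Secondary outcomes: 9.* Items 1 to 9 of SAP 5.2 apply to both groups: mortality, out-of-territory ischemic stroke, disabling stroke, TIA, unplanned revascularization, myocardial infarction, composite vascular events, EQ-5D and mRS. Item 10 (periprocedural) is left out because it concerns the procedure; SAP 7.5 Safety Analyses says "Procedure-related complications in the endovascular recanalization group will be analyzed". Item 11 is left out because it presupposes a treated vessel; Protocol 3.9.2 says "Restenosis is defined as >50% stenosis within or immediately adjacent (within 5 mm) of the treated segment".
- *Interactions: 12.* Eleven factors, with time from event split twice: 10 + 2 = 12.
- *Pooled: 9 + 12 = 21.* This is a minimum. SAP 7.5 Safety Analyses adds between-group tests of adverse events, and SAP 7.7 Concomitant Medication and Risk Factor Management adds more.

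**Independent tests, all null hypotheses true**

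P(at least one P<0.05 among k tests) = 1 − 0.95^k

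| Tests | k | Calculation | Result |
|---|---|---|---|
| Secondary outcomes | 9 | 1 − 0.630 | 37.0% |
| Interactions | 12 | 1 − 0.540 | 46.0% |
| Pooled | 21 | 1 − 0.341 | 65.9% |

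Expected false positives among 21 tests: 21 × 0.05 = 1.05. Counting time from event once gives 43.1% for 11 interactions and 64.2% for 20 tests pooled.

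**Correlated tests**

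The tests overlap, so independence gives too high a figure. A simulation used 200,000 draws of equally correlated normal statistics. The correlations are assumptions; the documents give none.

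| Between-test correlation | 9 tests | 12 tests | 21 tests |
|---|---|---|---|
| 0.3 | 32.7% | 39.5% | 55.6% |
| 0.5 | 26.9% | 31.9% | 43.1% |
| 0.7 | 20.3% | 23.2% | 29.4% |

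If only the secondary outcomes are correlated (0.3 to 0.7) and the interactions are independent of them and of each other, the pooled figure is 1 − (1 − 0.327) × 0.540 = 64% down to 1 − (1 − 0.203) × 0.540 = 57%.

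**Effect of matching**

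The matched cohort is drawn from the full cohort, so its tests are not independent extra tests. With an assumed full-versus-matched correlation of 0.7 to 0.9 and a between-test correlation of 0 to 0.7, repeating the nine secondary outcomes gives about 54% down to 27%.

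For the primary outcome alone, accepting significance in either cohort gives about 8.3% (correlation 0.7) to 7.0% (correlation 0.9) rather than 5%. SAP 7.5 Primary Efficacy Outcome already plans a log-rank test, an unadjusted Cox model and an adjusted Cox model, and the matching section repeats the outcome analysis. None of these is named as decisive.

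**The case against.** The strongest reply is that leaving secondary outcomes unadjusted beside a single primary is common practice, and that this plan does set the primary apart. SAP 3 states a hypothesis for the primary outcome only, SAP 6 ties the comparison of interest to it, and SAP 7.7 Secondary Outcomes already plans hazard ratios with 95% CIs. All of that is true, and it is why the primary needs no adjustment for other endpoints. It does not remove the rule that P<0.05 is significant for every statistic, or the significance purpose given to each interaction model.

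A second reply is that the tests overlap. The vascular composite contains several other secondary outcomes, an mRS of 6 is death, and the two time splits are nested. This stands and lowers the figures, as the ranges show.

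A third is that treatment is chosen by patients or their representatives, so a 5% error rate per between-group test assumes no residual confounding. This also stands: the percentages describe chance alone.

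A reader might infer three stronger points that the documents do not support:

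- *The interaction tests are also repeated after matching.* The matching sections name baseline characteristics and outcome only.
- *A false positive is more likely than not.* Each family alone stays below 50% even under independence. The pooled figure exceeds 50% under independence, at a common correlation of 0.3, or if the interactions are near-independent, but not at 0.5 or 0.7.
- *The primary result is invalidated.* Nothing here shows that.

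**Conclusion.** The concern holds for secondary and subgroup results. The plan judges at least 21 between-group and interaction tests at unadjusted 0.05, under reasoning that covers only the primary outcome, and without an exploratory label. With no true effects, the chance of at least one P<0.05 among the 21 is 66% under independence and about 56% to 29% at an assumed common correlation of 0.3 to 0.7. Even the lowest figure is nearly six times the nominal 5% (29.4 / 5 = 5.9). The counts come from the documents; the correlations are assumed, and residual confounding is ignored.

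For the primary outcome, the open question is which of several planned analyses carries the claim.

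**What to change.** In SAP 7.1, replace both the sentence that makes every P<0.05 significant and the sentence that waives adjustment with:

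> A significance claim at two-sided 0.05 is made only for the single primary-outcome analysis named in advance. All other primary-outcome analyses, including those in the matched cohort, are supportive. Secondary outcomes and subgroup interactions are reported as estimates with 95% CIs, labelled exploratory, without significance wording.

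Then:

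1. Name that one analysis, chosen from those in SAP 7.5 Primary Efficacy Outcome and SAP 7.6 Propensity Score Matching Analysis.
2. Make the same restriction in Protocol 3.16.5 and in the P-value line of the synopsis.
3. In SAP 7.6 Subgroup Analysis, reword the purpose of the interaction models as estimating how the treatment effect varies, not judging significance.

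If any of these sentences is left as it is, the plan will contradict itself. The change needs no new data or analysis and avoids choosing an adjustment method. Its cost is that no formal significance claim can be made on secondary or subgroup results. If the sponsor wants such claims, the alternative is an adjusted level; Bonferroni would give 0.05/9 = 0.0056, 0.05/12 = 0.0042 or 0.05/21 = 0.0024 per test. Neither route deals with confounding.

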7.2 Data Handling Conventions

Premature withdrawal and missing data

If any subject withdraws prematurely from the study (prior to the final visit), they are required to complete the withdrawal visit in the case report form (CRF). The reasons for withdrawal will be presented in a summary table. For the purposes of summaries and analysis of clinic visit data, this visit will be assigned to the next scheduled clinic visit for that subject, regardless of whether the date falls within the next visit window.

Efforts will be undertaken at study sites to reduce the amount of missing data. For the primary efficacy outcome, multiple imputations in a model including strong prognostic variables will be used. Also, sensitivity analyses will be undertaken to explore the effect of missing data on the endpoint and test the robustness of the estimate. Ultimately, only patients who entirely completed the 1-year follow-up are included in the final analysis.

Event rates

The number of people and person-time of events should be recorded in detail and showing the event rate of each treatment group in summary statement.

The event rate for each treatment group will be calculated as: the sum of number of event for all the patients/the sum of number of treatment periods for all the patients.

Time to event analysis

Differences between treatments in the risk of any stroke (ischemic or haemorrhagic) event or composite vascular events during follow-up will be assessed using standard Kaplan-Meier time-to-event approaches. The time to the first event will be used in the model when there are multiple events of the same type. Patients will be considered censored at the time of study termination or death if there are no events occurred during the study.

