Exclusion Criteria	
 • (1) Severe stenosis or occlusion of other arteries, or tandem stenosis proximal to the qualifying artery. • (2) Intracranial hemorrhagic diseases such as definite Intracranial tumors, any intracranial vascular malformations, hemorrhagic transformation of infarction, spontaneous intracranial hemorrhage (cerebral parenchymal, subarachnoid, subdural, or epidural) within 30 days. • (3) Non atherosclerotic intracranial arterial disease: arterial dissection, moyamoya disease or moyamoya syndrome demonstrated by imaging examination, or a definite medical history of autoimmune vasculitis. • (4) Evidence of cardioembolic embolism such as atrial fibrillation, prosthetic valve(s), infective endocarditis, mitral stenosis, atrial myxoma, intracardiac clot or vegetation, left ventricular aneurysms and so on. • (5) Known unstable angina or myocardial infarction within the last 6 months. • (6) Intolerance or allergic reaction to any treatment-related medication, including aspirin, clopidogrel, heparin, and local or general anesthetics. • (7) History of life-threatening allergy to contrast dye. • (8) Severe liver impairment (AST or ALT > 3 times normal, cirrhosis), serum creatinine > 3.0 mg/dl. • (9) Past history of EC-IC bypass surgery or EVT. • (10) Major surgery (including open femoral, aortic, or carotid surgery) within previous 30 days or planned in the next 90 days after enrollment. • (11) Late-stage malignant tumors, cachexia, or other serious diseases and an expected life expectancy of less than 1 year. • (12) Pregnant, perinatal stage or lactating women.
Treatments and Study Groups	
The technical feasibility of ER for all sNA-IAO patients in this study will be collaboratively evaluated by two experienced interventional neuroradiologists. The decision to select either medical treatment alone or additional ER is made by the patients themselves or their legal representatives. Patients are subsequently divided into two groups based on selection of treatment approach: the medical group and the ER group.

Follow-up schedule	Baseline, 30±7 days, 90±7 days, 1 year±30 days
Primary Outcome	
The primary outcome is a composite outcome as follows:
 
 • Any stroke or death within 30 days after enrollment • Ischemic stroke in the territory of the qualifying artery from 30 days to 1 year after enrollment.

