3.8 Follow-up

All participants will be followed up by the neurologists at 30±7 days, 90±7 days, 1 year ±30 days. The preferred follow-up modality is to implement face-to-face clinical evaluations. At every scheduled follow-up visit, the participants' medication regimens, laboratory tests, risk factor management (as previously outlined), and potential adverse clinical events/outcomes are evaluated by an experienced neurologist and/or neurointerventionalist. When patients are unable to attend on-site clinical follow-ups, a remote telephonic follow-up will be utilized as an alternative method of patient assessment. During the 1-year follow-up period, all patients are required to undergo a neurovascular imaging examination including DSA, CTA or MRA.

For perioperative patients in ER group, a clinical examination including the National Institutes of Health Stroke Scale (NIHSS) and Glasgow Coma Scale (GCS) will be carried out at 24-72 hours after the procedure. Meanwhile, patients will undergo CT to assess the cerebral hemorrhage at 24-72 hours, if possible, supplementary assessment of vessel recanalization status will be conducted through CTA or MRA. At the one-week post-intervention assessment, a clinical evaluation will be conducted, including patients' clinical status, NIHSS score, GCS score, and adverse events.

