Medical treatment will be identical in both groups. Both groups are prescribed with an medical treatment (includes aspirin 100 mg per day for the entire follow-up and clopidogrel 75mg per day for the first 90 days after enrollment). In instances where clopidogrel pharmacogenetic resistance testing is performed, and the results demonstrate either a loss-of-function CYP2C19 allelic variant or an adenosine diphosphate (ADP)-induced platelet aggregation rate exceeding 40%, alternative antiplatelet agents such as ticagrelor or

cilostazol may be strategically implemented as therapeutic substitutes. Atorvastatin will be administered at a dosage of 20 mg to 80 mg per day for one year following enrollment, with the continuation of treatment thereafter contingent upon the patient's condition.

Risk factor management:

Risk factor management is based on 2014 American Heart Association/American Stroke Association guidelines¹ for the clinical management of cerebrovascular disorders. (details of risk factor control targets in Supplement 1)

Follow-up:

All participants will be followed up by the neurologists at 30±7 days, 90±7 days, 1 year ±30 days. All imaging studies will undergo blinded review by experienced neuroradiological experts (over 10 years in advanced neuroimaging evaluation experience). All those involved in the subsequent clinical and imaging assessment of outcomes will be blinded to treatment regime.

5. Outcomes

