7.7 Secondary Outcomes

Time-to-event secondary outcomes will be evaluated using Kaplan-Meier survival analysis and Cox regression model. HR between the two groups and its 95% CI will be calculated using a Cox proportional hazards regression model. Non-time-endpoints of the secondary outcomes will be evaluated using logistic regression model. The 1-year mRS score will be analyzed using ordinal logistic regression to estimate the common odds ratio (OR). The 1-year EQ-5D scores will be compared between groups using general linear regression analysis.

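### SAP 7.2 books a withdrawal visit as the next scheduled visit whatever its date, so values from about day 98 can be labelled 1-year data, and a completers-only rule in the same section conflicts with this

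*SAP*

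**What the plan says.** SAP 7.2 requires a withdrawal visit on the case report form for any subject who leaves before the final visit. It then says "this visit will be assigned to the next scheduled clinic visit for that subject, regardless of whether the date falls within" that visit's window. The scope is stated: "For the purposes of summaries and analysis of clinic visit data". The rule is therefore not confined to listings.

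The follow-up schedule in Protocol 3.8 is "30±7 days, 90±7 days, 1 year ±30 days". The Protocol synopsis and SAP section 4 give the same three visits. Nothing is scheduled between the 90-day and 1-year visits.

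SAP 7.7 (Secondary Outcomes) analyses the mRS at 1 year by ordinal logistic regression. For quality of life it says "The 1-year EQ-5D scores will be compared between groups using general linear regression analysis". Neither analysis states a minimum follow-up time.

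Two other statements in SAP 7.2 matter here. Multiple imputation is planned, but only for the primary efficacy outcome. The same paragraph closes by limiting the final analysis to patients whose 1-year follow-up is complete.

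**The concern.** A visit label should say when the measurement was made. This rule sets the plan's own windows aside for the patients whose timing is least regular. The schedule has one long gap, so a patient who leaves soon after the 90-day visit has the 1-year visit as the next one. A measurement taken about three months after enrollment can then carry a 1-year label.

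The outcomes exposed are those defined at a fixed time, namely the 1-year mRS and the 1-year EQ-5D. If early values enter those models, the estimates no longer describe status at 1 year, and any change after withdrawal goes unseen. Treatment is chosen by the patient or representative (Protocol 3.6), so withdrawal need not follow the same pattern in the two groups. Summaries by visit, including any that support the risk-factor comparison in the SAP, would take the same mislabelled values.

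The completers-only statement would exclude the same patients. Two analysts following the same SAP section could therefore produce different 1-year results.

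**Working it through.** The plan states no figure on this point, so there is nothing to reproduce. The check is window arithmetic, followed by a comparison of the two rules.

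**Inputs.** Visit days and tolerances are from Protocol 3.8 and SAP section 4. One year is taken as 365 days (assumption).

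**Windows** (target day minus and plus tolerance):
- 30-day visit: 30−7 = 23 to 30+7 = 37
- 90-day visit: 90−7 = 83 to 90+7 = 97
- 1-year visit: 365−30 = 335 to 365+30 = 395

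**How early a 1-year label can fall.** For a withdrawal visit on day d, with the 1-year visit next:

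| d | Situation | Before window opens (335−d) | Before day 365 (365−d) | Share of year elapsed (d/365) |
|---|---|---|---|---|
| 84 | day after a 90-day visit held on day 83 | 251 | 281 | 23% |
| 98 | first day after the 90-day window (97+1) | 237 | 267 | 27% |
| 334 | last day before the 1-year window | 1 | 31 | 92% |

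The stretch outside any window is days 98 to 334. That is 334−98+1 = 237 days, or 237/365 = 65% of the year.

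**The two rules side by side**, for a patient who withdraws on day 98 with an mRS recorded then:
- Assignment rule alone: the day-98 mRS is analysed as the 1-year mRS.
- Completers-only rule alone: the patient is left out of the final analysis. The assignment rule then has no role there and affects only other visit summaries.
- Both rules: the result depends on what counts as completing follow-up, which the SAP does not define. If it means actual follow-up to 1 year, the patient is dropped. If it means having data in the 1-year slot, the patient is kept with the day-98 value.

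**What cannot be computed.** The documents give no withdrawal rate, no split by group, and no mRS or EQ-5D values. The day counts measure how wrong the label can be. They do not measure the effect on an odds ratio or a mean difference.

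**The case against.** The strongest reply is the completers-only statement. A withdrawal visit exists only for someone who leaves before the final visit. Read literally, every patient touched by the assignment rule is outside the final analysis, and no day-98 value reaches the 1-year comparison. This stands as one reading. It does not settle the matter, because the SAP does not define completion, does not rank the two rules, and does not say whether the final analysis includes the secondary outcomes. If the completers-only rule does govern, the assignment rule has no use in that analysis and still mislabels visit summaries.

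A second reply also stands. Neither document says that the mRS or EQ-5D is recorded at the withdrawal visit. Table 1 of the Protocol has no column for it, and Protocol 3.10 lists no assessments for it. That these scales are collected there is an inference from their use at scheduled visits.

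Three stronger readings are tempting and are not supported:
- A reader might infer that the rule clashes with multiple imputation because the value is no longer missing. Imputation is planned only for the primary outcome, which is analysed as time to event. A visit label does not fill in missing event follow-up.
- A reader might infer that the bias differs between groups in a known direction. Self-selected treatment makes different withdrawal patterns possible, but the documents give no data on them.
- A reader might infer equal harm at the 90-day visit. A withdrawal on day 38 would be booked there 83−38 = 45 days before the window opens, but no listed outcome is fixed at 90 days, so only summaries are affected.

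**Conclusion.** The point holds in a limited form. As written, SAP 7.2 can give a 1-year label to data from about day 98, 237 days before the window opens, or from day 84 (251 days) after an early 90-day visit. It also contains a completers-only rule that would exclude the same patients, with no statement of which prevails or for which outcomes. The text needs correction whichever was intended.

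The exposure is two secondary outcomes, the 1-year mRS and EQ-5D, plus summaries by visit. For the two outcomes it depends on two conditions that the documents leave open: that the scales are recorded at withdrawal, and that the completers-only rule does not remove the patients. It would go too far to say that the reported 1-year results will contain early values. The time-to-event primary outcome is not directly affected by the assignment rule. The size and direction of any bias cannot be computed from the documents.

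**What to change.** Change SAP 7.2 as follows:

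1. Delete the rule that moves a withdrawal visit to the next scheduled visit. Count an assessment as a scheduled visit only if its date lies in the protocol window (days 23–37, 83–97 or 335–395, with 1 year as 365 days). Report other withdrawal visits under their own label with the actual day.
2. Where a withdrawn patient has no assessment in the 1-year window, treat the 1-year mRS and EQ-5D as missing. Extend multiple imputation to these two outcomes, with the withdrawal-visit value, where recorded, and its date as predictors. At present no missing-data method is named for either.
3. Restrict the completers-only statement to a sensitivity analysis and define completion by actual follow-up. Otherwise the imputed patients would be dropped again.
4. State whether the mRS and EQ-5D are recorded at the withdrawal visit.

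The cost is more missing 1-year values to impute and slightly more analysis work. The edit covers several sentences of SAP 7.2, with a matching line under Secondary Outcomes. No new data are needed.

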3.3 Participating Center Eligibility

To minimize selection bias, all participating centers are mandated to systematically enroll consecutive eligible patients according to predefined protocol criteria. To be fully eligible for participation in this study, participating centers selection are required to meet the following minimum criteria:(1) all study centers are required to have performed at least 120 endovascular procedures annually, including at least 40 cases of intracranial artery endovascular procedures; (2) the interventional neuroradiologists at these centers had each performed over 100 endovascular procedures..

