7.3 Study Population

The number of all participants included in the screening will be calculated. Listing will be presented for participants of deviations from the inclusion/exclusion criteria, the reasons for screening failures will also be documented. Based on all enrolled participants, the number and percentage of participants who completed the study and withdrew early, the number and percentage of participants who withdrew early for various reasons, as well as the number of participants who lost to 1-year follow-up, will be calculated and summarized. Finally, participant distribution flow chart will be presented.

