7.5 Primary Efficacy Outcome

The difference in primary outcome between groups was assessed using Kaplan-Meier analysis and compared via log-rank test. Hazard ratio (HR) between the two groups and its 95% CI will be calculated using a Cox proportional hazards regression model. Furthermore, a multivariate Cox proportional hazards model will be used to perform multivariable adjustment for the primary outcome, yielding the adjusted hazard ratio (aHR) and its 95% CI.

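### SAP 7.2 limits the final analysis to 1-year completers; read literally, this drops observed primary events, and it is not reconciled with the planned imputation or censoring

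*SAP*

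**What the plan says.** Three rules in SAP 7.2 (Data Handling Conventions) bear on patients without full follow-up.

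- Imputation: "For the primary efficacy outcome, multiple imputations in a model including strong prognostic variables will be used". Unspecified missing-data sensitivity analyses follow in the next sentence.
- Completers: "Ultimately, only patients who entirely completed the 1-year follow-up are included in the final analysis". No exception is made for patients who have already had a primary event, and no definition of completion is given.
- Censoring: "Patients will be considered censored at the time of study termination or death if there are no events occurred during the study". The paragraph is about any stroke and composite vascular events. It names study termination and death, but not loss to follow-up.

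The same section asks for follow-up time: "The number of people and person-time of events should be recorded in detail". SAP 7.5 (Primary Efficacy Outcome) is a time-to-event analysis: "The difference in primary outcome between groups was assessed using Kaplan-Meier analysis and compared via log-rank test", with Cox hazard ratios. SAP 7.3 will report "the number of participants who lost to 1-year follow-up", but does not assign those patients to an analysis set. Protocol 3.16 (Statistical Analyses) has no completers rule, no analysis-set definition and no missing-data rule.

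**The concern.** The primary outcome (SAP 5.1, Protocol 3.9.1) can be reached from the day of enrolment. A patient with an adjudicated stroke on day 20 who withdraws on day 120 has a fully known primary outcome, yet has not finished one year of follow-up. A literal reading of the rule discards that event.

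Completion happens after baseline and can depend on outcome. Selecting on it can distort the hazard ratio when the retention of patients with an event, relative to event-free patients, differs between groups. Treatment here is chosen by the patient, so there is no particular reason to expect equal retention. Propensity matching balances baseline variables and does not repair selection after enrolment. Protocol 3.3 shows that the sponsor cares about selection at entry ("To minimize selection bias, all participating centers are mandated to systematically enroll consecutive eligible patients"). That sentence is about enrolment rather than attrition, but a completion filter brings selection in by another route.

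The rule also collides with imputation. If patients without full follow-up are excluded, few or no missing primary outcomes remain to impute, and the SAP does not say which rule governs the primary estimate.

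**Working it through.** The documents give no sample size, event rate, death rate or loss rate, so there is no figure of the plan's own to reproduce. **Every input below is an assumption**, chosen to show the mechanism.

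**Inputs.** P = true 1-year primary risk, 12% in both groups unless stated. d = deaths by day 30, 2%, counted as completed. L1 = loss after a non-fatal primary event. L0 = loss of event-free patients, 5% unless stated.

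**Step 1: events removed.** Share of primary events removed = (P − d) × L1 / P.
- L1 10%: 0.10 × 0.10 / 0.12 = 8.3%
- L1 20%: 0.10 × 0.20 / 0.12 = 16.7%

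**Step 2: risk among completers.** Risk = [d + (P − d)(1 − L1)] / {d + (P − d)(1 − L1) + (1 − P)(1 − L0)}.
- L1 10%: 0.110 / (0.110 + 0.88 × 0.95) = 0.110 / 0.946 = 11.6%
- L1 20%: 0.100 / (0.100 + 0.836) = 0.100 / 0.936 = 10.7%

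The true value is 12.0%. These are proportions of patients; the SAP's own event rate divides by treatment periods, so they show only that reported rates would shift. With L1 20% in the endovascular group and 10% in the medical group, the risk ratio is 0.1068 / 0.1163 = 0.92 instead of 1.00.

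**Step 3: Cox hazard ratio, the planned estimate.** Expected counts by day over 365 days, with equal group sizes. Deaths are spread evenly over days 1–30; 40% of non-fatal events fall evenly on days 1–30 and the rest on days 31–365. With e the expected events, R the numbers at risk on each day, and subscripts 1 and 0 for endovascular and medical, the hazard ratio θ solves Σ{e₁ − (e₁ + e₀)R₁θ / (R₁θ + R₀)} = 0.

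| Loss after an event, endovascular vs medical | Completers-only HR, true 12% vs 12% | Completers-only HR, true 10% vs 12% |
|---|---|---|
| 10% vs 10% | 1.00 | 0.83 |
| 20% vs 20% | 1.00 | 0.83 |
| 20% vs 10% | 0.915 | 0.760 |
| 10% vs 20% | 1.093 | 0.905 |
| All enrolled, censored at last contact | 1.00 | 0.83 |

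In the 12% vs 12% column, an early share of 20% or 70% instead of 40% leaves 0.915 unchanged to three decimals. With 1% deaths instead of 2%, the unequal cases become 0.905 and 1.105.

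**Step 4: only event-free loss differs.** Let L0 be 5% (endovascular) vs 10% (medical), spread evenly over the year, with L1 10% and P 12% in both groups.
- Loss unrelated to later risk: completers-only 0.963 (reversed 1.038); all enrolled 1.00.
- Loss confined to patients who would never have had an event: completers-only 0.951 (reversed 1.052); all enrolled 0.985 (reversed 1.015).

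Censoring therefore recovers the true value in the first case and comes closer to it in the second.

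**The case against.** **Completion may be meant more generously.** The sponsor could count a patient with a primary event, or a death, as completed. No section says so, and the wording makes no exception. This stands as a reason to describe the deletion as the literal reading, not as settled practice.

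**Censoring may already be planned.** Study termination could mean the patient's own exit. That is possible, but the paragraph names other endpoints and does not mention loss. It leaves three rules unreconciled instead of resolving them.

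**Follow-up may be nearly complete.** Protocol 3.8 provides telephone contact when a visit is impossible, and SAP 7.2 requires a withdrawal visit. Both may reduce loss or its effect, and the assumed 10–20% loss after an event may be too high. Neither changes who is excluded.

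**Sensitivity analyses and the flow chart will show the exclusions.** They would make them visible but would not correct the main estimate.

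Three stronger inferences are tempting but unsupported.
- That the rule favours endovascular treatment: the illustration moves either way, and equal loss after an event leaves the hazard ratio essentially unchanged.
- That 30-day deaths will be dropped: the mortality outcome, death as score 6 on the modified Rankin Scale, and the mention of death in the censoring sentence suggest this is not intended. It needs stating, nothing more.
- That imputation is the wrong primary approach: where loss relates to prognosis, it can be defended against simple censoring. That choice is the sponsor's.

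**Conclusion.** Wrong as written. The completers sentence is current text, nothing in either document exempts observed events, and followed literally it discards information that the planned log-rank and Cox analyses can use. The textual conflict is certain; the bias is not. Under the assumptions above, a 10-point difference in loss after an event moves a true hazard ratio of 1.00 to 0.915 or 1.093, and one of 0.83 to 0.760 or 0.905. Equal loss after an event costs events and shifts rates, with essentially no change in the hazard ratio. These sizes rest on assumed risks and losses and on counting deaths as completed; they are not estimates for this study. Nor should a reader infer that censoring removes all bias: that requires event-free loss to be unrelated to later risk.

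**What to change.** In SAP 7.2:

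1. Delete the completers-only sentence and define the primary analysis set as all enrolled patients.
2. Count every primary event observed up to last contact, including death to day 30. Censor event-free patients at last contact, or at death after day 30.
3. State whether multiple imputation for patients lost while event-free is the primary analysis or a sensitivity analysis. In either role, observed events are kept.
4. If a completers analysis is wanted, label it a sensitivity analysis in which a primary event or a death counts as completed.
5. State that the same set definition applies to the matched analysis. SAP 7.6 (Propensity Score Matching Analysis) carries over methods but says nothing about who is included.

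The cost is SAP wording and a small amount of extra analysis. The time-to-event methods are already planned and person-time is already to be recorded.
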